5.4. Estimated Duration of Patient Participation

Patients will be enrolled in the trial for a period of up to 125 days, which includes up to 20 days of post-removal follow-up prior to study discharge.

6. SCHEDULE OF ASSESSMENTS

Refer to Section 12.1 of the protocol for the schedule of assessments.

7. ANALYSIS POPULATIONS

The following populations will be considered for the summarization and analysis of the data from this study:

Intention to Treat Population

The Intention to Treat (ITT) population includes The ITT population will consist of any enrolled patient who underwent an attempted Spanner device implant procedure. This population will be used for all of the analyses unless otherwise stated.

Per Protocol Population

The Per Protocol (PP) population will consist of all patients who are enrolled in the study, have been implanted with a Spanner device, and have completed all study visits with no major protocol deviations while enrolled in the study. A major protocol deviation is defined as any protocol deviation that may affect the primary endpoint. The PP population will only be used as an analysis population if the ITT population produces unexpected results that could have been caused by protocol deviations.

Safety Population

The safety population will consist of all subjects who are enrolled in the study.

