14.6.1 Analysis Populations

The following analysis populations will be defined.

- Intent-to-Treat (ITT) Population – The ITT population will consist of any enrolled subject who underwent an attempted Spanner device implant procedure.
- Per Protocol (PP) Population – The PP population will consist of all subjects who are enrolled in the study, have been implanted with a Spanner device, and have completed all study visits with no major protocol deviations while enrolled in the study².
- Safety Population – The safety population will consist of all subjects who are enrolled in the study.

The analysis of the primary and secondary efficacy endpoints will be conducted on ITT and PP populations. The primary analysis set will be the ITT analysis. All safety analyses will be conducted on the safety population.

The study subjects to be excluded from the PP analysis set and the reasons for their exclusion will be determined and documented prior to statistical analysis. These decisions will not be outcome-data driven.

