13.2. Primary Effectiveness Endpoint Analysis

The results of the Primary Effectiveness Endpoint analysis will be presented in the SRS TLF, Table 31.

The primary effectiveness endpoint for this study is the proportion of patients who achieve adequate bladder drainage over 90 days, defined as a post-void residual (PVR) of ≤ 150 ml. The pre-specified success criterion for this study is that ≥ 50 percent of patients will achieve adequate bladder drainage at each of the 4 evaluations over 90 days. The primary objective will be met if the one-sided lower bound of the 95% confidence limit for the incidence of patients who achieve adequate bladder drainage at each of the 4 evaluations over 90 days is $\geq 50\%$. The null and alternative hypotheses are as follows:

$$H_0: \pi \leq 0.5$$

$$H_a: \pi > 0.5$$

π is the proportion of patients with maintenance of successful voiding during the Spanner implantation period.

Results based on the ITT population will be presented in Table 32 entitled *Primary Effectiveness Endpoint Analysis* (PVR of ≤ 150 ml) (ITT population). The table will contain the point estimate and the confidence limit based on patients who met the primary endpoint.

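### SAP 7 runs the per-protocol analysis only after an undefined trigger (an unexpected ITT result that deviations might explain), while protocol 14.6.1 plans it unconditionally for the primary and secondary endpoints

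*SAP*

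**What the plan says.** Protocol 14.6.1 is unconditional: "The analysis of the primary and secondary efficacy endpoints will be conducted on ITT and PP populations". It ranks the two sets: "The primary analysis set will be the ITT analysis". It also requires PP exclusions and their reasons to be settled and documented before the statistical analysis, adding "These decisions will not be outcome-data driven".

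SAP 7 makes ITT the default ("This population will be used for all of the analyses unless otherwise stated") and then adds a restriction: "PP population will only be used as an analysis population if the ITT population produces unexpected results that could have been caused by protocol deviations". PP members must be implanted and "have completed all study visits with no major protocol deviations while enrolled in the study".

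The SAP's results sections do not restore the protocol's plan. For the primary endpoint, SAP 13.2 names one population: "Results based on the ITT population will be presented in Table 32". SAP 13.3, on the secondary endpoints, names none, so the ITT default applies. SAP 13.4 describes both ITT and PP for the exploratory endpoints and attaches no trigger.

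**The concern.** A supportive analysis is informative when it is reported whatever it shows. Under SAP 7, someone looks at the ITT result, decides whether it is unexpected, decides whether deviations could explain it, and only then is PP used. Neither document defines either judgement, gives it a direction or says who makes it.

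The protocol's safeguard covers who is in PP. It does not cover whether PP is run or shown, which is the part SAP 7 leaves until after the result.

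At stake is the credibility of the supportive evidence. A reader who sees a PP table cannot tell whether it would have appeared had ITT come out otherwise. A reader who sees none cannot tell whether PP would have disagreed. The SAP also ends up assuring PP for its least important endpoints while leaving it optional for the primary one.

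**Working it through.** The plan gives no figure on this point to reproduce. The check is a comparison of the texts, followed by an illustration.

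**1. Can both rules be followed?** For the primary and secondary endpoints:

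| ITT result | Protocol 14.6.1 | SAP 7 |
|---|---|---|
| As expected | PP analysed | PP not used |
| Unexpected, not explainable by deviations | PP analysed | PP not used |
| Unexpected, explainable by deviations | PP analysed | PP used |

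They agree in one row of three. For the exploratory endpoints SAP 13.4 describes PP in every row, which also sits badly with SAP 7.

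**2. Can the trigger be applied in advance?** No. Its input is the ITT result, and neither half has a criterion.

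**3. Illustration of how far PP and ITT can differ.**

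Inputs from the documents:
- 105 subjects and 20% dropout (protocol 14.2, SAP 5.3): 0.20 × 105 = 21, and 105 − 21 = 84.
- Subjects who miss any of Visits 1–4 or withdraw are failures (SAP 4.2.1). PP drops them.
- Null rate 50% and an exact binomial test at one-sided 0.025 (protocol 14.6.3). SAP 13.2 uses the "one-sided lower bound of the 95% confidence limit", which corresponds to one-sided 0.05.

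Assumptions: all 105 are in ITT; the 21 are exactly those who do not complete Visits 1–4; PP has no other exclusions; there are 53 successes (chosen for illustration).

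Formula: p = Σ C(n,k) × 0.5ⁿ, summed over k from x to n.
- ITT: 53/105 = 50.5%. With n = 105, the counts 53 to 105 are exactly the upper half of a symmetric distribution, so p = 0.50.
- PP: 53/84 = 63.1%, p = 0.0107.
- Gap: 63.1 − 50.5 = 12.6 percentage points. ITT misses both thresholds; PP nominally meets both.

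**4. Dependence on the missing-data rule.** SAP 8 bases the primary presentation on observed data and makes failure imputation a sensitivity analysis. SAP 5.3 defines dropouts as leaving before 90 days without a PVR failure. Such subjects have no known outcome, so under SAP 8 they leave both sets: 53/84 in each, gap zero. Only subjects who withdraw or miss a visit after a PVR failure would separate the sets, and the documents give no count of these. In the protocol, 14.11 multiply imputes while 14.3 makes withdrawal a failure, so it does not settle the size of the gap either.

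**5. Does the gap measure the trigger?** No. If PP is always reported, the results are still 53/105 and 53/84. The gap comes from the PP definition combined with counting non-completers as failures. The trigger governs only whether the second figure is seen.

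**The case against.** The strongest reply is that little turns on this. ITT is primary, the secondary endpoints are descriptive with no formal test (SAP 4.1), and PP membership is fixed before analysis. All of that stands, and it limits the point to reporting.

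Two stronger readings are tempting. A reader might infer that a favourable PP result could rescue a failed ITT result and so inflate type I error. Neither document has such a rule: the protocol makes ITT the primary set, and the SAP's named primary table is ITT. A reader might also take the 12.6 points as the damage done by the trigger; step 5 shows it is not. Nor is 53/105 clearly a case that would fire the trigger. With 65% success among 84 completers and dropouts counted as failures, the plan's own assumptions imply 0.65 × 84/105 = 52% in ITT. In addition, the illustration contains no deviations beyond any missed visits.

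Other safeguards may be cited. Protocol 14.10 says departures from the planned analysis will be described and justified, but only where required, and its heading refers to the SAP. An analyst who followed SAP 7 might therefore report nothing. Protocol 14.7 leaves the secondary analysis to the SAP, but that does not reach the primary endpoint or withdraw the population commitment in 14.6.1. SAP 7 openly discloses the condition, which helps a reader who sees a PP table but not one who sees none. The table templates cited in SAP 3.2 are not available here and may include PP tables for these endpoints; if so, they would themselves conflict with SAP 7.

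**Conclusion.** The conflict is real and rests on the wording alone. Protocol 14.6.1 and SAP 7 cannot both be followed unless the ITT result meets a condition that nobody can apply in advance, and SAP 13.4 departs from that condition too. The consequence is result-dependent display of a supportive analysis. Formal success and type I error are unaffected.

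The effect of selective display cannot be quantified from the documents. The illustrated difference between the sets (50.5% against 63.1%) depends on SAP 4.2.1 applying, 21 non-completers and no other PP exclusions. It falls to zero for the planned dropouts under SAP 8. Confidence is high on the conflict; its practical impact is modest.

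**What to change.** In SAP 7, delete the sentence that makes PP conditional. State in its place that PP is always reported for the primary and secondary endpoints, as supportive only, with success judged on ITT, as protocol 14.6.1 plans. Name the PP results in SAP 13.2 and 13.3.

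The cost is a wording change and one or two extra tables that the protocol already foresees. PP membership must be derived anyway, because SAP 9 tabulates disposition for the PP population. The downside for the sponsor is that PP must be shown whichever way it differs from ITT.

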8. ANALYSIS CONVENTIONS

Specific algorithms are discussed for imputing missing or partially missing dates, if deemed appropriate, under specific data topics. Imputed or derived data will be flagged in the individual patient data listings. Imputed data will not be incorporated into any raw or primary datasets. These data are retained in derived (or analysis) datasets.

Total duration on study will be calculated as the difference between the date of informed consent and the last on-study observation. All calculations defining the duration on study will be performed relative to the date of informed consent and follow the algorithm $DURATION = [STUDY\ COMPLETION\ OR\ WITHDRAW\ DATE - INFORMED\ CONSENT\ DATE]$.

General Conventions for Summarization

Summary statistics will consist of the number and percentage of responses or counts at each level for categorical variables (e.g. race). For continuous variables, and the sample size (n), mean, median, standard deviation (SD), minimum, and maximum values will be presented.

All mean and median values will be formatted to one more decimal place than the measured value. Standard deviation values will be formatted to two more decimal places than the measured value. Minimum and maximum values will be presented with the same number of decimal places as the measured value.

The number and percentage of responses will be presented in the form XX (XX.X%).

All probability values will be rounded to 4 decimal places; however, the number of digits to be displayed in the CSR tables will depend on the parameter and result. All probability values that round to 0.0000 will be presented as '<0.0001' and p-values that round to 1.0000 will be presented as '>0.9999'. Probability values < 0.05 will be considered to be statistically significant.

- All summary tables will include the analysis population sample size (i.e., number of patients).
- Relative Study Day 1 is defined as the day the patient underwent the initial study procedure. All study days are determined relative to the day the patient underwent the study procedure.
- Baseline values will be defined as those values recorded immediately prior to the study procedure.
- Change from baseline for ratio data will be calculated as follows:
$$\text{Change} = \text{Post-baseline value} / \text{baseline value}.$$
- Change from baseline for differences will be calculated as follows:
$$\text{Change} = \text{Post-baseline value} - \text{baseline value}.$$
- Missing data may have an impact upon the interpretation of the trial data. The primary presentation of the results will be based on the observed data only. A sensitivity analysis (worst-case) will be performed by imputing the outcome for the primary and secondary endpoints as *failures* for the binary outcomes if the patient misses an evaluation visit or if the patient withdraws prematurely prior to attending the required visits. Section 14.11 of the protocol contains a discussion on the use of multiple imputation.
- Date variables will be formatted as DDMMYY for presentation.
- SAS® Version 9.2 or more recent, or a similar statistical package will be the statistical software package used for all data analyses.
- All data from this study will be presented in a listing. All listings will be sorted by patient number and visit date, as applicable.
- Table and listing numbering will follow ICH guidelines for post-text table and listing numbering.

Handling of Missing or Partial Dates for Adverse Events

If a portion of the start date of an adverse event is missing, or the entire date is missing, and the missing portion results in the treatment emergent determination being indeterminate, the adverse event will be considered *treatment emergent*.

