14.1 Level of Significance, Power and Sample Size

A hypothesis test that the proportion of successes in the treatment group is statistically significantly greater than 50% will be computed. In order to have an 80% chance of showing that the success proportion in the Spanner group is statistically significantly greater than 50%, assuming that the device can achieve a 65% success rate, with $\alpha=0.05$, a sample size of $n=85$ completers will be needed for the study. The sample size calculation was based on an exact binomial one sample test.

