14.2 Expected Drop-out Rates

Assuming a dropout rate of 20%, the total sample size of $n=105$ subjects will be required for the study. A hypothesis test that the proportion of successes in the treatment group is statistically significantly greater than 50% will be computed.

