14.3 Primary Effectiveness Variable and Pass/Fail Criteria

The primary effectiveness endpoint is the success/failure of the subject to have a successful urinary void at all four study visits: (a) upon initial placement of the first stent (Visit 1), and (b) at all three visits in which the subject has a stent placed for 30 days (Visits 2, 3 and 4).

The primary effectiveness endpoint will be marked as a failure for a subject if any of the following occur:

- PVR of >150 ml at any visit (Visits 1, 2, 3, and 4)
- The subject withdraws from the trial

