14.11 Treatment of Missing Data, Including Lost to Follow-up and Withdrawals

For endpoint evaluations subjects with missing data due to missed visit, lost-to-follow-up or study withdrawal will have their missing data imputed using a multiple imputation method. Unless otherwise specifically noted, no statistical techniques will be used to impute missing values in other analyses of study data.

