4.2.1. Primary Effectiveness Endpoint

PVR levels will be monitored throughout the 90 days of stent use to confirm that the patient is able to successfully empty his bladder. PVR levels are assessed on Visits 1, 2, 3 and 4 while stent is in place using abdominal ultrasound. The hypothesis is that over 90 days of stent use, 50% of the patients will be able to successfully empty their bladder, as defined by PVR of ≤ 150 ml at all four visits.

Patients where the PVR is >150 ml at 1 or more of the 4 visits will be considered a *treatment failure*. Patients who fail to attend any of the 4 scheduled visits, or withdraw prematurely, will also be treated in primary the analysis as a *treatment failure*. Patients where the PVR is <150 ml at all 4 visits will be considered a *treatment success*.

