5.3. Sample Size Justification

In order to have an 80% chance of showing that the success proportion in the Spanner group is statistically significantly greater than 50%, assuming that the device can achieve a 65% success rate, with a two-sided type 1 error rate of 5%, a sample size of $n=85$ completers will be needed for the study. Assuming that a one-sided type 1 error rate of 5% will be adequate, the sample size of 85 completers will provide 88% power. Completers are those subjects whose endpoint is known at 90 days.

Assuming a dropout rate of 20%, the total sample size of $n=105$ patients will be required for the study. Dropouts are those patients who exit the study prior to completing 90 days without experiencing a PVR failure. The sample size calculation was based on an exact binomial one sample test using PASS 14.0.9 (PASS 14 Power Analysis and Sample Size Software (2015). NCSS, LLC. Kaysville, Utah, USA, ncss.com/software/pass.)

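### The primary endpoint has three conflicting missing-data rules; on the plan's own planning numbers, observed-data analysis passes and failure scoring fails

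*SAP*

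**What the plan says.** Three rules are given for the same endpoint.

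- **Failure scoring.** SAP 4.2.1 counts non-attendance and withdrawal as failure: "Patients who fail to attend any of the 4 scheduled visits, or withdraw prematurely, will also be treated in primary the analysis as a" (the sentence closes by labelling these patients failures). Protocol 14.3 lists, next to a PVR above 150 ml at any visit, "The subject withdraws from the trial". It does not list a missed visit.
- **Observed data.** SAP 8: "The primary presentation of the results will be based on the observed data only". The next sentence there names the primary and secondary endpoints and makes failure scoring a worst-case sensitivity analysis.
- **Multiple imputation.** Protocol 14.11: for endpoint evaluations, subjects with data missing due to "missed visit, lost-to-follow-up or study withdrawal will have their missing data imputed using a multiple imputation method". No imputation model is given. SAP 8 only refers the reader to that section.

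SAP 13.2 names the ITT population and a one-sided lower confidence bound for the primary result, but gives no rule for a missing outcome.

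The sample size is built on completers. SAP 5.3: "Completers are those subjects whose endpoint is known at 90 days", and "Dropouts are those patients who exit the study prior to completing 90 days without experiencing a PVR failure". Protocol 14.1 plans 85 completers, "assuming that the device can achieve a 65% success rate". Protocol 14.2 then allows for 20% dropout to reach 105.

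**The concern.** The same procedure is the primary analysis in one SAP section and a sensitivity analysis in another, and the protocol adds a third method. With a single arm and a fixed goal there is no comparator in which missing data could partly cancel out. Dropping missing patients from the denominator gives a success rate at least as high as counting them as failures. In an open-label trial, an unresolved choice of this kind could be settled after the results are visible.

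The sample size adds to the problem. A subject who leaves without a PVR failure is left out of the 85 completers in SAP 5.3, but under SAP 4.2.1 that subject has a known outcome, namely failure. The stated power therefore belongs to the observed-data analysis and does not describe the primary analysis in SAP 4.2.1.

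**Working it through.** **Inputs.** Null 50%; assumed success 65%; 85 completers; 20% dropout; 105 enrolled (Protocol 14.1–14.2, SAP 5.3). Exact binomial test at one-sided 0.025 (Protocol 14.6.3). One-sided 95% lower bound at or above 50% (SAP 4.1 and 13.2), read here as one-sided 0.05. Paired results below are for 0.025 / 0.05.

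**1. The plan's own figure.** The one-sample normal approximation gives n = [(1.96 × 0.5 + 0.842 × √(0.65 × 0.35)) / 0.15]² = 84.8, so 85. Power at 85 is 80.1% / 88.0%, matching the stated 80% and 88%. The exact test that the documents name gives 73.6% / 86.0% at 85; that is a separate point. For dropout, 105 × 0.80 = 84, which is consistent with 105 enrolled. All of this counts known outcomes only.

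**2. Planning case.** 105 treated, 84 known, 0.65 × 84 = 54.6, so 55 successes. The p-value is P(X ≥ 55 | n, 0.5).

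| Rule | Rate | Exact one-sided p | Lower bound, 97.5% one-sided | Result |
|---|---|---|---|---|
| Observed data | 55/84 = 65.5% | 0.003 | 54.3% | pass |
| Missing = failure | 55/105 = 52.4% | 0.348 | 42.4% | fail |

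The one-sided 95% lower bounds are 56.0% and 43.9%, so the verdicts are the same at 0.05. With 85 known outcomes, 55/85 gives p = 0.0044 and the same verdict.

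**3. Where the rules part.** At N = 105 the smallest passing count is 64 / 62. Holding observed success at about 65%, failure scoring first misses 0.025 at 8 dropouts (63/105, p = 0.0252) and 0.05 at 11 dropouts (61/105, p = 0.059). Observed-data analysis passes throughout.

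**4. Tipping point.** From 55/84 observed, 64 − 55 = 9 of the 21 missing (43%) must count as successes to pass at 0.025, and 62 − 55 = 7 of 21 (33%) at 0.05. This is a count threshold and ignores between-imputation variance.

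**5. Passing when the failure-scored rate is exactly 50%.** Let dropout be d, completers n ~ Bin(105, 1 − d), completer success q = 0.5/(1 − d), and c(n) the exact critical count. The observed-data pass probability is Σ P(n) × P(X ≥ c(n) | n, q).

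| d | q | 0.025 | 0.05 |
|---|---|---|---|
| 20% | 0.625 | 59% | 71% |
| 10% | 0.556 | 16% | 25% |
| 5% | 0.526 | 6% | 11% |

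**6. Power of failure scoring at N = 105.** This is P(X ≥ 64 or 62 | 105, p).

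| Meaning of 65% | p | 0.025 | 0.05 |
|---|---|---|---|
| Already counts dropouts as failures | 0.65 | 83% | 92% |
| Completer rate, 5% dropout | 0.65 × 0.95 = 0.6175 | 61% | 75% |
| Completer rate, 10% dropout | 0.65 × 0.90 = 0.585 | 34% | 50% |
| Completer rate, 20% dropout | 0.65 × 0.80 = 0.52 | 4% | 9% |

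For 80% power at 20% dropout, completer success would have to be about 80% / 78%.

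**The case against.** The three rules do not carry equal weight. The endpoint definition in SAP 4.2.1 and the pass/fail list in Protocol 14.3 are specific and point to failure scoring, and both documents make ITT primary. The SAP 8 sentence is one bullet among general conventions and could be a leftover. This helps in choosing the right rule, but it does not remove the conflict. The SAP 8 text names the primary endpoint and expressly demotes failure scoring, and ITT fixes who is analysed, not how a missing outcome is scored.

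The planning case is also one scenario. It takes 65% as a completer rate and uses the full 20% dropout. At 5% dropout the pass rates in step 5 fall to 6% and 11%, and under the other reading of 65% the power is adequate. Both points stand, but SAP 5.3's definitions favour the completer reading, and 20% is the plan's own allowance.

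Finally, the worst-case analysis is already planned, so both numbers would be reported. That is true, but the plan would still not say which one decides the trial.

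One caution on motive. Protocol 21.5 keeps many subjects in the study after stent removal, and a subject withdrawn under the PVR criterion of Protocol 21.5.8 is already an observed failure. Dropout linked to device intolerance is plausible, but the documents give no figures for it.

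**Conclusion.** The plan is wrong as written: the primary endpoint has no single rule for missing outcomes, and the stated power belongs to only one of the competing rules.

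The reversal in the planning case rests on 65% being a completer rate and on 20% of subjects leaving without a PVR failure. It does not depend on whether one-sided 0.025 or 0.05 is used. The pass rates in step 5 are false passes only if failure scoring is the target, as SAP 4.2.1 says for withdrawal and missed visits and Protocol 14.3 says for withdrawal.

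Failing here means failing the formal test or the lower-bound rule. An estimate of 52.4% would meet the bare statement in Protocol 8.1 that at least half of subjects succeed, but SAP 4.1 and 13.2 tie success to the lower bound. The result under multiple imputation cannot be predicted, because no model is given.

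**What to change.** - State one primary rule in both documents and repeat it in SAP 13.2: ITT population, with withdrawal or a missed visit scored as failure. Add the missed visit to Protocol 14.3.
- Say how a visit attended without a stent in place is scored. Protocol 21.5 allows such visits, while Protocol 8.3.1 and SAP 4.2.1 assess PVR with the stent in place.
- In SAP 8, relabel the observed-data result as a sensitivity analysis.
- In Protocol 14.11, limit multiple imputation to a sensitivity analysis and name its model. Add a tipping-point table.
- In Protocol 14.1–14.2 and SAP 5.3, restate power under the chosen rule with the exact test, and say whether the 65% already counts dropouts as failures.

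**Cost.** The changes are to wording in SAP 5.3, 8 and 13.2 (and 4.2.1 for visits without a stent) and Protocol 14.1–14.3 and 14.11, with no new data items per subject. Protocol section 16 requires FDA approval of changes that may affect scientific soundness, so a supplement may be needed. The headline success rate becomes less favourable. If 65% is a completer rate, power at 105 is well below 80% at the planned dropout, and the sponsor must justify or reconsider the sample size.
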